2.3 POOLING OF CENTERS

This multicenter study is to be conducted at approximately 6 sites in the United States. No significant differences between centers are anticipated. Data from all centers will be pooled for analysis.

2.4 MULTIPLE COMPARISONS/MULTIPLICITY

All analyses of study data will be descriptive. No adjustments for multiple comparisons will be made.

2.5 EXAMINATION OF SUBGROUPS

No subgroup analyses are planned for this study.

3 DATA HANDLING CONVENTIONS

3.1 DERIVED AND TRANSFORMED DATA

3.1.1 Baseline Definition

The Baseline Visit is defined as Visit 2 (Week/Day 0). Baseline values for non-seizure efficacy and safety assessments will be the last values collected prior to the first administration of IP (i.e., GNX), unless otherwise specified.

Baseline seizure frequency data is collected during the four weeks between the Screening Visit (Visit 1, Week -4) and the Baseline Visit (Visit 2, Day 0). This interval may range from no less than 28 days to no more than 32 days.

3.1.2 Study Day

For reporting purposes, Study Day will be calculated from the date of the Baseline Treatment Visit (Visit 2, Week/Day 0). Similarly, Study Week will be calculated from the date of the Baseline Treatment Visit.

For all assessments performed on or after the first day of treatment, i.e. reference date \geq date of first dose of IP, Study Day is calculated as:

- Study Day = (date of assessments/events - first day of treatment) + 1

For assessments performed prior to the first day of treatment, i.e. reference date $<$ date of first dose of IP, Study Day is calculated as:

- Study Day = date of assessment/event – first day of treatment.

3.1.3 Derivations

3.1.3.1 Baseline seizure frequency

Baseline 28-day seizure frequency will be calculated as the total number of primary seizures in the baseline period, i.e. between screening (Visit 1, Week -4) and baseline treatment (Visit 2, Week/Day 0), divided by the number of days with non-missing seizure data in the baseline period, multiplied by 28.

$$\text{Baseline seizure frequency} = \frac{\text{\# seizures, baseline period}}{\text{\# baseline period days with seizure data}} \times 28$$

3.1.3.2 Post-baseline seizure frequency – Maintenance Period, Part A, Part B and Overall

Post-baseline 28-day seizure frequency will be calculated as the total number of seizures in the specified post-baseline period divided by the number of days with non-missing seizure data in the same post-baseline period, multiplied by 28. Within Part A of the study, post-baseline seizure activity will be determined based on the days following the first day after the date of the first dose of IP. The first day of treatment is included in neither the baseline nor the post-baseline period since seizures reported on that date could have occurred either before or after the initiation of treatment. Within Part B (OLE

period), post-baseline seizure activity will be determined by the first day of OLE treatment.

Separate frequencies will be calculated for the 8-week maintenance period of Part A (Maintenance), Parts A (12-week treatment period consisting of a 4-week titration period and an 8-week maintenance period) and B of the study (OLE period of up to 24 weeks) and across both study parts.

Post-baseline specified study period 28-day seizure frequency =

$$\frac{\# \text{ seizures, specified study period}}{\# \text{ specified study period days with seizure data reported}} \times 28$$

3.1.3.3 Percent change in 28-day seizure frequency – Maintenance Period, Part A, Part B and Overall

% change from baseline =

$$\frac{[(\text{post-baseline 28-day seizure frequency}) - (\text{baseline 28-day seizure frequency})]}{(\text{baseline 28-day seizure frequency})} \times 100$$

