Any patient not tolerating the next dose step can be maintained at the lower dose step for additional days before advancing to the next dose. If the next dose is still not tolerated, the patient can drop back to the next lower dose step. A minimum dose of 33 mg/kg/day or 900 mg/day is generally required following the escalation period, during the maintenance period.

Dose changes including alternative dosing paradigms (e.g., lower dose during the daytime and higher dose in the evening) should be discussed with the sponsor medical monitor prior to making the change or within 48 hours of making the change. However, the final decision to adjust drug dosages lies with the investigator. For any patient who is unable to be maintained at the minimum dose, the investigator should contact the sponsor medical monitor to discuss continued IP dosing. Patients who discontinue GNX treatment before the completion of the maintenance period in Part A will continue to be followed per protocol and, at a minimum, patients will be encouraged to maintain daily seizure diary entries until Part A is completed.

During Part B, patients who meet all of the inclusion criteria and none of the exclusion criteria will initiate treatment in Part B with GNX at the same dose they were on at the completion of Part A. During Part B, doses of GNX may be adjusted to a maximum of 600 mg three times daily (TID) for patients weighing > 28 kg and a maximum dose of 21/mg/kg TID for patients weighing ≤ 28 kg.

Duration of treatment: After 4 weeks of baseline seizure charting, patients will initiate a 4-week GNX titration period followed by an 8-week GNX maintenance period (Part A). Patients completing Part A and deemed eligible for Part B will continue taking GNX. Patients will have the option to continue longer-term treatment on ganaxolone until commercially available or the study is terminated by the Sponsor. Anyone discontinuing GNX will undergo a 2-week taper and a 2-week follow-up safety visit.

The planned study duration is approximately 64 weeks for patients who stay on the study through Part B.

Criteria for Evaluation:

Seizures: All seizure types and number of seizures will be recorded daily in a diary. Days in which no seizures occur will also be noted. Subsets of seizure types will be defined below.

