Primary Efficacy Endpoint: The primary efficacy endpoint is the percent change in 28-day primary seizure frequency through the end of the 12-week treatment period (4-week titration and 8-week maintenance) relative to the 4-week baseline. The primary seizure types are defined as the following: focal motor seizures without impairment of consciousness or awareness, focal seizures with impairment of consciousness or awareness, focal seizures evolving to bilateral, tonic-clonic seizures, and generalized motor seizures including tonic-clonic, bilateral tonic, bilateral clonic, and atonic/drop seizures. Focal aware non-motor and generalized seizures without motor features, infantile or epileptic spasms, and myoclonic seizures are not considered primary seizure types.

[figure not shown]
Post-baseline 28-day seizure frequency will be calculated as the total number of seizures in the 12-week treatment period (4-week titration and 8-week maintenance periods) divided by the number of days for which seizure data are reported in that period, multiplied by 28. Baseline 28-day seizure frequency will be calculated as the total number of seizures in the baseline period divided by the number of days for which seizure data are reported in the baseline period multiplied by 28. Descriptive statistics will be used to summarize changes in seizure frequency. No inferential statistical testing will be performed.

Secondary Efficacy Endpoints (Seizure control): Derived seizure secondary efficacy endpoints will be based on data through the end of the 12-week treatment period relative to the 4-week prospective baseline period.

- Percentage of patients experiencing a $\geq 50\%$ reduction in 28-day primary seizure frequency through the end of the 12-week treatment period compared to the 4-week Baseline Period.

Secondary Efficacy Endpoints (Other):

- CGI-I, parent/caregiver and clinician
- CGI-C - Target Behavior

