9.6.1. Primary Efficacy Endpoint

The primary efficacy endpoint (change in seizure frequency) is the percent change in 28-day seizure frequency through the end of the 12-week treatment period (4-week titration and 8-week maintenance) relative to the baseline, based on the primary seizure types. The primary seizure types are defined as the following: focal motor seizures without impairment of consciousness or awareness, focal seizures with impairment of consciousness or awareness, focal seizures evolving to bilateral, tonic-clonic convulsive seizures, and generalized motor seizures including tonic-clonic, bilateral tonic, bilateral clonic, or atonic/drop seizures. Focal aware non-motor and generalized seizures without motor features, infantile or epileptic spasms, and myoclonic seizures do not count as the primary seizure types.

Post-baseline 28-day seizure frequency will be calculated as the total number of seizures in the 12-week treatment periods (4-week titration plus 8-week maintenance period) during Part A divided by the number of days with seizure data in the period, multiplied by 28. Baseline 28-day seizure frequency will be calculated as the total number of primary seizures in the baseline period divided by the number of days with seizure data in the baseline period, multiplied by 28.

$$\left(\frac{[(\text{Post-baseline 28-day seizure frequency}) - (\text{Baseline 28-day seizure frequency})]}{(\text{Baseline 28-day seizure frequency})} \right) \times 100\%$$

The baseline, post-baseline, and arithmetic and percent changes from baseline in 28-day seizure frequency will be summarized using descriptive statistics.

The percentages of seizure-free days will be based on the primary seizure types (primary seizure-free-days) and infantile/epileptic spasms (infantile/epileptic spasms free days).

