1.2.5 Open-Label Extension Endpoints

To evaluate the secondary study objectives of assessing the long-term efficacy and safety of GNX, the following endpoints defined above for Part A of the study will be examined in patients participating in Part B of the study:

- Primary seizure frequency during OLE: change in 28-day primary seizure frequency from baseline (Visit 1 to Visit 2) to the OLE period (Visit 5 through Visit 8)
- Percent change in primary seizure frequency during OLE relative to the baseline period.
- Primary seizure frequency across 12-week treatment period and OLE: change in 28-day primary seizure frequency from baseline (Visit 1 to Visit 2) to the cumulative treatment periods A and B (Visit 2 through 8)

- Percent change in primary seizure frequency baseline versus cumulative treatment periods (12-week treatment period + OLE)
- Seizure frequency for all types of seizures in OLE versus baseline and cumulative treatment Parts A and B versus baseline
- Percent change in all-types seizure frequency in OLE versus baseline and cumulative treatment Parts A and B versus baseline
- CGI-C for target behaviour: Week 36 and final visit of the OLE
- CGI-I, parent/caregiver and clinician: Week 36 and final visit of the OLE.
- [REDACTED] at the final OLE visit.
- Safety endpoints listed in [Section 1.2.4](#).

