4.2 EFFICACY ANALYSES

4.2.1 Primary Efficacy Analysis

4.2.1.1 Primary Analysis

The primary efficacy endpoints, the percent change in 28-day primary seizure type frequency through the end of the 12-week treatment period (Part A; 4-week titration and 8-week maintenance) relative to the baseline, is defined in Section 1.2.1. The calculation of the primary endpoint is described in Section 3.1.3.

Descriptive summaries including the number of patients with non-missing primary seizure data, mean arithmetic change and percent change in 28-day primary seizure type frequency from baseline and associated 95% confidence intervals, SD, minimum, median and maximum values will be presented for the baseline period, 4-week titration period, 8-week maintenance period and 12-week treatment period. All patients in the ITT population and all available seizure data within Part A of the study will be included in these analyses regardless of whether the patient stopped taking IP or took rescue medication.

Additionally, a by-patient listing of seizure data collected during Part A will be provided.

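### The seizure-frequency derivations name primary seizures at baseline but unqualified seizures afterwards, and the all-type extension endpoints have no visibly defined matching baseline

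*SAP*

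**What the plan says.** **SAP derivations.** Section 3.1.3.1 states: "Baseline 28-day seizure frequency will be calculated as the total number of primary seizures in the baseline period". The formula displayed under that sentence counts seizures without naming a type. Section 3.1.3.2 states: "Post-baseline 28-day seizure frequency will be calculated as the total number of seizures in the specified post-baseline period", and neither the sentence nor its formula restricts the type. Section 3.1.3.3 subtracts the first quantity from the second and divides by the first.

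**Protocol.** Section 9.6.1 pairs the same two wordings: primary seizures at baseline and, after baseline, the "total number of seizures in the 12-week treatment periods". The synopsis repeats this pair under Statistical Methods (Primary Endpoint: Definition and Analysis). The other synopsis paragraph, Primary Efficacy Endpoint under Criteria for Evaluation, is unqualified in both periods; its baseline sentence reads "Baseline 28-day seizure frequency will be calculated as the total number of seizures in the baseline period".

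**What is intended.** SAP 4.2.1.1 describes the primary endpoint as "the percent change in 28-day primary seizure type frequency through the end of the 12-week treatment period". SAP 1.2.1, 1.2.2.1 and 4.2.2.1 likewise name primary types for the primary and 50% responder endpoints. SAP 1.2.1 and 4.2.1.1 both send the reader to 3.1.3 for the calculation.

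**All-type endpoints.** SAP 1.2.5 lists all-type seizure frequency and "Percent change in all-types seizure frequency in OLE versus baseline and cumulative treatment Parts A and B versus baseline".

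**What is in the data.** The synopsis says "All seizure types and number of seizures will be recorded daily in a diary". Spasms, myoclonic seizures, focal aware non-motor seizures and generalized non-motor seizures are therefore in the diary but outside the primary set.

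**The concern.** A percent change is meaningful only if the same events are counted in both periods. As worded, the derivation puts a restricted count in the denominator and an unrestricted count in the numerator. Any non-primary seizure after baseline then looks like worsening, whatever the drug does.

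The primary endpoint has text elsewhere that settles the meaning. The all-type endpoints in SAP 1.2.5 have less to lean on: they need an all-type baseline frequency, and the only one that 3.1.3 puts into words is primary-only. The SAP does make the distinction elsewhere, since 3.1.3.4 defines baseline seizure-free days separately for all types and for primary types.

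The study is uncontrolled and descriptive, with about 30 treated patients. The summarised percent changes are its efficacy result, and no comparison arm would reveal a counting artefact.

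**Working it through.** The plan states no figure to reproduce, so the check applies the formula in SAP 3.1.3.3 directly.

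**Inputs**
- P = baseline primary frequency per 28 days. The entry minimum is 8 in the 4-week baseline (protocol 4.1, criterion 5); P cancels from the percentages below.
- q = ratio of baseline non-primary to baseline primary seizures. *Assumption*: the documents give no value, so 0 to 1.0 is shown.
- N0 = qP, the baseline non-primary frequency.
- P1, N1 = post-baseline primary and non-primary frequencies.

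**Formulas**
- As worded: 100 × [(P1 + N1) - P]/P
- Matched, primary in both periods: 100 × (P1 - P)/P
- Matched, all types in both periods: 100 × [(P1 + N1) - (P + N0)]/(P + N0)

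**Error against the primary-matched score:** the difference is 100 × N1/P. It is never negative, and it is zero only when there are no non-primary seizures after baseline.

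**Error against the all-type-matched score:** the difference is 100 × (P1 + N1) × N0/[P(P + N0)], again never negative. If both groups of seizures fall by the same fraction r, then P1 + N1 = (1 - r)P(1 + q), and the expression becomes 100 × (1 - r)q. That equals 100 × N1/P, so the two errors coincide.

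**Worked case**, P = 8, q = 0.5, everything halved. Baseline is 8 primary and 4 non-primary; post-baseline is 4 and 2.
- As worded: (6 - 8)/8 = -25%
- Primary in both periods: (4 - 8)/8 = -50%
- All types in both periods: (6 - 12)/12 = -50%

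**Score as worded over the assumed range of q**

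| q | No true change | All types halved | Primary halved, non-primary unchanged |
|---|---|---|---|
| 0 | 0% | -50% | -50% |
| 0.1 | +10% | -45% | -40% |
| 0.25 | +25% | -37.5% | -25% |
| 0.5 | +50% | -25% | 0% |
| 1.0 | +100% | 0% | +50% |

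In the first two scenarios either matched rule gives 0% and -50% at every q. In the third, the primary-matched score is -50% throughout.

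**Is an all-type baseline defined anywhere visible?** SAP 3.1.3 runs unbroken from 3.1.3.1 to 3.1.3.7. It contains one baseline seizure frequency, worded on primary seizures. The all-type definition in 3.1.3.4 concerns seizure-free days, not frequency.

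**The case against.** The strongest reply is that *seizures* is shorthand. The formula in SAP 3.1.3.1 uses the unqualified noun directly beneath a sentence that says primary seizures, so the SAP seems to use the two interchangeably. Protocol 9.6.1 opens by basing the endpoint on primary types, and protocol 7.5.1 lists the types that count towards it. SAP section 7 places detailed programming specifications in a separate document. A programmer reading the whole SAP would probably filter to primary types. For the primary endpoint this stands: intent is clear and only the derivation needs correcting.

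A reader might infer that the 50% responder rate and the 35% criterion for Part B will also be miscounted. The documents do not support that. SAP 1.2.2.1 and 4.2.2.1 define response on primary seizures. The Part B criterion in protocol 4.1.1 is stated on primary seizures and confirmed at Visit 5; nothing ties that check to SAP 3.1.3.2.

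A reader might also infer that nothing anywhere defines an all-type baseline. That goes too far. The SAP's exploratory endpoint section is blacked out, as is a section between 4.3.6 and 4.5, and either could bear on it. Comparing all types with baseline also most naturally means all types in both periods. What remains is narrower: the derivation section is visible and complete, and its wording gives the all-type endpoints a primary-only baseline.

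Finally, the study is descriptive with no hypothesis tests, so no error rate is affected. That limits the stakes, but the descriptive estimates still have to be right.

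**Conclusion.** The inconsistency is literal and should be corrected. For the primary and responder endpoints it is a drafting defect in the derivation, not a wrong endpoint. For the all-type extension and cumulative endpoints it matters more, because 3.1.3 as worded gives the wrong comparison and no visible text supplies the right one.

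The direction is certain: applied as worded, the rule can only shift percent change towards worsening. The size cannot be found from the documents because the non-primary share is not given. It is zero for a patient with no non-primary seizures; at the top of the assumed range (q = 1.0), a true halving of all seizures would score as no change. These figures are illustrations that depend on the assumed ratio and on literal programming, not predictions of what the analysis will show.

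**What to change.** **SAP 3.1.3.1 to 3.1.3.3.** Define baseline and post-baseline 28-day frequency for a named seizure set, the same set in both periods, and carry it into the displayed formulas. The set is primary types for the primary and responder endpoints, and all types for the all-type endpoints in 1.2.5.

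**SAP 4.2.2.1.** Point the percent-reduction reference to 3.1.3.3. It now points to 3.1.3.6, which concerns seizure-free days.

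**Protocol 9.6.1 and synopsis, Statistical Methods.** Insert *primary* in the post-baseline sentence of each.

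**Protocol synopsis, Criteria for Evaluation, Primary Efficacy Endpoint.** Insert *primary* in both the baseline and the post-baseline sentence. Adding it only after baseline would create the reverse mismatch: with no true change the score would be 100 × [P - P(1 + q)]/[P(1 + q)] = -100 × q/(1 + q), a false improvement of 33.3% at q = 0.5.

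**Cost.** A few sentences in the SAP and single-word insertions in the protocol. The diary already records every type, so no new data are needed.

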3.1.3.4 Frequency of seizure-free days per 28 days – Baseline

The frequency of seizure-free days per 28 days total for all seizure types during the baseline period will be calculated as the total number of days reported as seizure-free, i.e., with seizure diary response to “Did you have seizures on this date?” equal to “no” or with no approved seizures for a date, multiplied by 28, and divided by the number of days with non-missing seizure data in the baseline period.

Baseline seizure-free days per 28-day period

$$= \frac{\# \text{ seizure-free days, baseline period} \times 28}{\# \text{ baseline period days with seizure data}}$$

The frequency of seizure-free days per 28 days total for the primary seizure types only will be calculated in the same manner except defining seizure-free as days with seizure diary response to “Did you have seizures on this date?” equal to “no” or with a response to this question equal to “yes” but no primary seizure types reported and approved for that day.

3.1.3.5 Frequency of seizure-free days per 28 days – Part A, Part B and Overall

The percentage of post-baseline seizure-free days per 28 days total within a specified post-baseline study period will be calculated as the

Post-baseline specified study period seizure-free days per 28-day period

$$= \frac{\# \text{ seizure-free days, specified study period} \times 28}{\# \text{ specified study period days with seizure data}}$$

3.1.3.6 Percent change from baseline in seizure-free days per 28 days

The percent change from baseline in seizure-free days will be

$$\frac{[(\text{post-baseline seizure-free days}/28 \text{ days}) - (\text{baseline seizure-free days}/28 \text{ days})]}{(\text{baseline seizure-free days per 28 days})} \times 100$$

% change from baseline in seizure-free days per 28 days =

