3.3.2 Missing Seizure/Medication Diary Entries

The calculation of seizure frequency endpoints will include only days for which diary entries are available. Missing seizure data will not be imputed.

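### Percent change in seizure-free days (SAP 3.1.3.6) is undefined for a patient with no seizure-free day at baseline and unstable for one with very few

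*SAP*

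**What the plan says.** SAP 3.1.3.6 begins "The percent change from baseline in seizure-free days will be" and gives post-baseline minus baseline seizure-free days, divided by "baseline seizure-free days per 28 days", times 100. It has no rule for a baseline of zero. SAP 2.1 and 3.3 summarize observed data only, without imputation.

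The input comes from SAP 3.1.3.4. For all seizure types it "will be calculated as the total number of days reported as seizure-free", meaning a diary answer of no "or with no approved seizures for a date". That count is multiplied by 28 and divided by the days that have diary data. For primary seizure types, a day qualifies if the diary answer is no, or is yes "but no primary seizure types reported and approved for that day".

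SAP 3.3.2 adds: "The calculation of seizure frequency endpoints will include only days for which diary entries are available".

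Protocol 9.6.1 describes a different measure: "The percentages of seizure-free days will be based on the primary seizure types", and also on infantile or epileptic spasms. That is a percentage of days, not a percent change from baseline.

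Protocol 4.1, inclusion criterion 5, requires at least 8 primary seizures over the 4-week baseline, with at least one in 3 of the 4 weeks. It sets no maximum and does not require a seizure-free day.

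**The concern.** A ratio to the patient's own baseline works only if that baseline is well away from zero. The entry criteria secure this for seizure frequency, which has a floor of 8. They do not secure it for seizure-free days, where the patients with the most frequent seizures sit at or near zero. Those patients either have no value or have one that swamps the others. The all-seizure-types version is the more exposed: spasms, myoclonic seizures and other non-primary types do not count towards eligibility, but each can remove a free day. At stake is whether this summary describes the treated group, or only those whose seizures left some free days at baseline.

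A smaller question concerns the all-seizure-types numerator. Its second limb does not itself mention a diary entry, while the denominator counts only days with data.

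**Working it through.** The documents give no result, target or power figure for this variable, so there is nothing to reproduce. The check evaluates the SAP's formulas directly.

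**1. Zero and small baselines.** Percent change = (post − base) / base × 100, in days per 28.
- Base 0, post 8: 8/0, undefined.
- A gain of 4 days: 4/1 = +400%; 4/2 = +200%; 4/5 = +80%; 4/10 = +40%; 4/20 = +20%.
- Largest possible value from 1 day: (28 − 1)/1 = +2700%; from 14 days: (28 − 14)/14 = +100%.

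**2. Effect on a mean of 30 (constructed illustration).** Suppose 29 patients go from 20 to 24 days (+20% each) and one goes from 1 to 5 (+400%). The mean is (29 × 20 + 400)/30 = 32.7% and the median is 20%, although every patient gained 4 days.

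**3. How often a zero baseline might occur.** The documents give no baseline rate distribution. As an assumption, let daily counts be Poisson with f seizures per 28 days. The chance of no free day in 28 is (1 − exp(−f/28))^28.

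| f per 28 days | Chance of no free day |
|---|---|
| 8 | about 0 |
| 28 | 0.000003 |
| 56 | 0.017 |
| 84 | 0.24 |
| 112 | 0.60 |

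If all 30 patients had 56 per 28 days, the chance of at least one undefined value would be 1 − (1 − 0.017)^30 = 0.40. Clustering at the same frequency leaves more free days and lowers these figures. A strictly regular pattern raises them: one seizure every day is only 28 per 28 days and leaves no free day.

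**4. Absolute change.** Post minus base gives +8.0 days for the patient in step 1 with a zero baseline, and +4.0 for each of the 30 patients in step 2.

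**5. The all-seizure-types numerator.** Take 28 dates, 20 of them with diary data and 8 without an entry.
- 5 answers of no: 5 × 28/20 = 7.0 if only diary days count; (5 + 8) × 28/20 = 18.2 if dates without an entry also count.
- 15 answers of no: 15 × 28/20 = 21.0 against (15 + 8) × 28/20 = 32.2, which is impossible on a 28-day scale.

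The wording should therefore exclude the second reading explicitly.

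**The case against.** The strongest reply is that little depends on this variable. It is not the primary endpoint, a listed secondary endpoint or a listed extension endpoint, and no visible analysis in SAP section 4 uses it. The exploratory text is redacted, so a rule for zero baselines may stand there. SAP 2.1 also reports the number of non-missing observations, the median and the quartiles by default. Undefined values would show as a lower n, and the median resists extreme ratios. All of this stands and limits the reach. It does not repair the formula: a lower n does not show that the missing patients are those with no free day, and a median of defined values still leaves them out.

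A reader might infer three stronger things that the documents do not support.
- *That the plan counts dates without a diary entry as seizure-free.* The all-seizure-types definition speaks of days reported as seizure-free, the primary-type version needs a diary answer, and SAP 2.1 uses observed data only. SAP 3.3.2 points the same way, although it names seizure frequency endpoints rather than seizure-free days. This is loose wording in one definition, not a rule.
- *That patients with no baseline free day will certainly be enrolled and silently lost.* They may enrol. Under the assumed model the chance is negligible at or below about one seizure a day, and the default n would reveal the loss.
- *That the 50% responder endpoint uses this formula*, because SAP 4.2.2.1 cites 3.1.3.6. The same sentence concerns reduction in seizure frequency, whose formula is in 3.1.3.3, so this is most likely a separate cross-reference slip.

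**Conclusion.** The point holds for the formula. As written, SAP 3.1.3.6 gives no value to an eligible patient with seizures on every baseline day, and gives disproportionate values to those with one or two free days. That follows from the text and needs no model. How many patients are affected is unknown. The range of about 0 to 60% across 8 to 112 seizures per 28 days rests on assumed rates and independent Poisson days, and matters only well above one seizure a day. The consequence is confined to a variable outside the primary and listed secondary endpoints. The numerator issue is a wording clarification for the all-seizure-types definition only.

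**What to change.** In SAP 3.1.3.6, replace the percent change with the absolute change in seizure-free days per 28 days, post-baseline minus baseline. It is defined at a zero baseline for every patient with diary data in both periods. It is also closer to the percentages of seizure-free days in Protocol 9.6.1, since days per 28 is the same proportion on another scale.

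In SAP 3.1.3.4, limit the second limb of the all-seizure-types definition to dates with a diary entry, so that numerator and denominator cover the same days.

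The cost is SAP wording and the matching derivation. Both inputs are already derived in 3.1.3.4 and 3.1.3.5. No new data are needed and study conduct does not change.
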